5.1 Nonclinical Pharmacology

5.2 Nonclinical Safety Pharmacology

5.3 Nonclinical Pharmacokinetics

5.4 Nonclinical Toxicology

5.5 Clinical Studies

5.5.1 Study MT-2990-E01

Protocol MT-2990-A01 Confi Protocol Amendment 4, v 5.0, dated 04March2020

6 OBJECTIVES AND ENDPOINTS

Overall, the objective of the study is to evaluate the safety and efficacy of MT-2990 in patients with surgically diagnosed endometriosis, experiencing moderate to severe endometriosis related pain and impact on quality of life.

6.1 Study Objectives

6.1.1 Primary Objective

• To assess the efficacy of MT-2990 on nonmenstrual pelvic pain in women with endometriosis

6.1.2 Secondary Objectives

- To assess the efficacy of MT-2990 on dysmenorrhea in women with endometriosis
- To assess the effect of MT-2990 on dyspareunia
- To assess the safety and tolerability of MT-2990

6.1.3 Exploratory Objectives

6.2 Study Endpoints

6.2.1 Primary Endpoint

[figure not shown]
• Mean change from Baseline to Week 16 in nonmenstrual pelvic pain

6.2.2 Key Secondary Efficacy Endpoints

[figure not shown]
• Mean change from Baseline to Week 16 in dysmenorrhea

6.2.3 Secondary Efficacy Endpoints

• Mean change from Baseline to Week 16 in dyspareunia score

- Mean change from Baseline to Week 16 in dysmenorrhea
- Mean change from Baseline to Week 16 in dyspareunia score

6.2.4 Safety Endpoints

[figure not shown]
- Physical examination (including breast examination)
- Vital signs (blood pressure, pulse rate, and tympanic body temperature)
- ECG parameters (including cardiac intervals: heart rate, PR, QRS, QT, QTcF and QTcB)
- Clinical laboratory assessments (hematology, biochemistry, coagulation, and urinalysis)
- TEAEs

6.2.5 Exploratory Endpoints

Protocol MT-2990-A01

Confidential

Page 32 of 103

[figure not shown]

7 STUDY DESIGN

7.1 Overall Study Design

7.1.1 Study Methodology

This is a Phase 2, randomized, double-blind, placebo-controlled study, stratified by moderate or severe pain to evaluate safety and efficacy of MT-2990 in women with endometriosis-associated moderate to severe pain. Approximately 76 subjects will be randomized into the study, with approximately 38 subjects in each treatment arm. The approximate duration of the study per subject is 52 weeks, inclusive of the Screening period, Double-blind Treatment period, and the Extended Follow-up period.

Following the Screening period, eligible subjects who have met all the eligibility criteria and have moderate or severe nonmenstrual pelvic pain, and dysmenorrhea will be randomized into the study. Approximately 38 subjects per arm will be enrolled. Subjects will be randomly allocated to 1 of 2 treatment groups (placebo or MT-2990 in a ratio of 1:1.

All efficacy and safety measures will be collected during the 16-week Double-blind Treatment period.

End-of-treatment (EOT) will occur at Week 12 (Visit 7) and primary and secondary efficacy endpoints will be assessed at the Week 16 (Visit 9) visit. Subjects who discontinue from the study will complete the procedures for Visit 9 within 10 days of discontinuation (or as soon as possible after the site becomes aware of the discontinuation).

During the Extended Follow-up period, visits will be conducted via a telephone call at Week 27 (Visit 10) and at Week 38 (Visit 11).

The Sponsor will be unblinded after Week 16 (Visit 9), while the Sites and subjects will remain blinded until the end of the Extended Follow-up period at Week 38 (Visit 11). During the study, database will be locked twice: at Week 16 (Visit 9) to assess safety and efficacy, and at Week 38 (Visit 11) to assess other outcomes during the Extended Follow-up period.

There will be 3 interim assessments for safety. The first interim assessment for safety will be performed when 20 subjects are randomized and have completed the Week 2 visit. The second interim assessment for safety will be performed when 50% of the subjects are randomized and have completed the Week 4 visit. The third interim assessment for safety will be performed when 50% of the subjects are randomized and have completed the Week 16 visit.

Serious adverse events (SAE) will be collected from the time of signing the ICF. All adverse events (AEs) will be collected from Day 1 through the Double-blind Treatment period (Visit 9). All fractures will be collected as events of special interest (AESI).

Blood and urine samples will be obtained at protocol prespecified time points for chemistry, hematology, and PK. Subjects will be required to undergo TVU during Screening and at the Week 16 visit.

The study does not require a laparoscopy procedure or dual-energy x-ray absorptiometry (DEXA) scan at any time during or after the study. All laparoscopic procedure data will be collected from the most recent laparoscopy procedure as well as any clinically indicated laparoscopy performed during the Double-blind Treatment period and Extended Follow-up period.

If available, data will be collected from the most recent DEXA scan (within 1 year of Screening) and any DEXA scan conducted during the Double-blind Treatment period and Extended Follow-up period.

The study design is presented in Figure 1.

[figure not shown]

Figure 1 Study Design Schematic

7.2 Rationale for Study Design and Treatment Regimens

The objectives of this study are to obtain efficacy, safety, and tolerability data for MT-2990 when administered as multiple doses in women with endometriosis experiencing endometriosis related pain.

Women with laparoscopically diagnosed endometriosis with moderate or severe endometriosis-associated pain will be enrolled into the study. Moderate-severe pain subset is an appropriate target, as these patients will likely have been laparoscopically diagnosed and progressed through first line therapies (e

In an attempt to assess the baseline pain scores, at least 2 menstrual cycles with an interval of 21 to 38 days documented within the Screening period up to 100 days will be required.

Primary and secondary endpoints are subject centric and will evaluate the pain associated with endometriosis. Nonmenstrual pelvic pain is to be evaluated as the primary endpoint and dysmenorrhea will be evaluated as the key secondary endpoint. Although there are no established guidelines for endometriosis related pain, American Society for Reproductive Medicine recommends the daily rating of pelvic pain and daily rating of dysmenorrhea as primary outcome measures. ¹⁹ Subjects will use the electronic (e)-Diary to report daily assessments of nonmenstrual pelvic pain and dysmenorrhea

Pharmacokinetic data from this study will be used in combination with other clinical studies for population PK analysis.

7.2.1 Risk:Benefit Statement

Treatment of moderate to severe pain related to endometriosis is a significant unmet need. Young women at childbearing age develop endometriosis related pain and other complications which effects their productivity at peak age.

The current study will evaluate the effect of MT-2990 on treatment of moderate to severe endometriosis related pain. This study will evaluate if MT-2990 may treat the endometriosis related pain.

MT-2990 is a human IgG1 monoclonal antibody that highly and specifically binds to IL-33 among IL-1 family molecules. It is under investigation for the potential clinical benefits for the treatment of moderate to severe endometriosis-related pain in women with surgically diagnosed endometriosis.

[figure not shown]
The overall nonclinical safety data and profile is supportive of the clinical use of MT-2990 in human clinical trials. Nonclinical studies have demonstrated no significant toxicity of MT-2990.

In the 1 clinical study conducted to date, single doses of MT-2990 were considered to be safe and well tolerated in healthy male subjects. No deaths, SAEs, AEs leading to withdrawal, or severe TEAEs occurred during the study.

The Sponsor will undertake all reasonable measures, to minimize the risk to subjects. Subjects will receive no further dosing if they meet any of the withdrawal criteria listed in Section 8.5.

This study will provide additional efficacy and safety information on the risk:benefit profile of MT-2990.

7.2.2 Rationale for Dose Selection

8 SELECTION AND WITHDRAWAL OF SUBJECTS

The Sponsor does not operate a Protocol waiver system for eligibility criteria.

8.1 Number of Subjects

Approximately 76 subjects will be randomized into the study, with approximately 38 subjects in each treatment arm.

8.2 Recruitment Methods

Subjects will be recruited via a variety of methods including, but not limited to, site review of subject records, media advertising, Contract Research Organization, and recruitment vendors, if appropriate. All recruitment material will be approved by Institutional Review Board (IRB) prior to implementation.

A sufficient number of subjects will be screened to ensure that the planned sample size is achieved. Only subjects who are eligible for the study will be enrolled.

8.3 Subject Inclusion Criteria

1. Subject must sign the written informed consent form (ICF) to participate in this study.

Inclusion Criteria for Entry into the Washout Period (if applicable [in addition to Inclusion Criteria 5 through 9]):

3. Subject agree to approximately 90-day washout interval of hormonal therapies, if applicable.

[figure not shown]
Inclusion Criteria for Entry into the Screening Period

- 4. Subject undergoing the Washout period (if applicable), must have a menstrual cycle with an interval of 21 to 38 days prior to entering the Screening period.
- 5. Subject must have a body mass index < 45 kg/m² (inclusive) at Screening and Day 1.
- 6. Subject who has documented surgical/laparoscopy diagnosis of endometriosis within 10 years of the Screening period.
- 8. Subject agrees to use 2 forms of nonhormonal contraception throughout the study (refer to Section 8.6.2).

9. In the Investigator's opinion, subject is able to understand the nature of the study and any risk involved in participation and is willing to cooperate and comply with the protocol restrictions and requirements including TVU.

Inclusion Criteria for entry into the Double-blind Treatment Period

11. Subject must have had 2 menstrual cycles with an interval of 21 to 38 days prior to treatment Day1.

8.4 Subject Exclusion Criteria

- 2. Subject is pregnant, breast feeding, or planning a pregnancy within the next 12 months.
- 3. Subject is < 6 months postpartum, postabortion, or postpregnancy at the time of entry into the Screening period.
- 4. Subject has a hormonal intrauterine device (IUD). If the hormonal IUD is removed prior to Screening and subject completes Washout period, subject will be eligible for study participation.

[figure not shown]
7. Subject with aspartate aminotransferase (AST), alanine aminotransferase (ALT), or total bilirubin ≥2.0 × upper limit of normal (ULN) above the reference range any time prior to randomization.

- 9. Subject with immunosuppression due to underlying medical condition;
 - a. Hereditary or congenital immunodeficiencies, cellular immunodeficiencies, hypogammaglobulinemia, or dysgammaglobulinemia
 - b. Current or anticipated use (within 6 months of randomization) of disease modifying doses of anti-rheumatic drugs (eg, azathioprine, cyclophosphamide, cyclosporine, methotrexate), or immunotherapy such as tumor necrosis factor (TNF)-α or interleukin (IL) inhibitors use within 12 weeks of the Screening visit.
 - c. History of solid organ or bone marrow transplantation.
 - d. Long term use $(\geq 7 \text{ days})$ of oral or parenteral glucocorticoids at a dose of ≥ 20 mg/day of prednisone equivalent within 12 weeks of the Screening visit.

- 13. Subject with QTcF or QTcB \geq 450 msec or clinically important abnormal findings on the ECG during the Screening visit.
- 14. Subject is not up-to-date on breast screening according to current guidelines.

Protocol MT-2990-A01

Confidential

Page 40 of 103

- 17. Subject has a surgical history of:
 - a. hysterectomy (with or without oophorectomy);
 - b. bilateral oophorectomy;
 - c. any other recent major surgery (including laparotomy for endometriosis) within 6 months or any minor surgery (including laparoscopy for endometriosis) within 3 months prior to Treatment Day 1, or scheduled for a surgical procedure during the course of study.
- 18. Subject is require more than 2 weeks of continuous use of prohibited long-acting narcotic or immediate release narcotic for treatment of endometriosis-associated pain within 6 months of entry into the Washout period (if applicable) or Screening period.
- 19. Subject has chronic pelvic pain for nonendometriosis related causes (eg, interstitial adenomyosis. pelvic inflammatory diseases, chronic nonendometriosis-related pelvic adhesive disease, irritable bowel syndrome, and other nonendometriosis related causes), which require systemic pharmaceutical chronic therapy for pain.
- 20. Subject with other chronic pain syndrome (eg, fibromyalgia, chronic back pain, myofascial pain syndrome, chronic headaches, and other chronic pain) which requires chronic analgesic or other chronic therapy.
- 22. Subject with a clinically significant gynecologic condition identified on the TVU during the Screening period such as:
 - Complex ovarian cyst > 3 cm or simple ovarian cyst > 5 cm that persists on repeat TVU;
 - Clinically significant endometrial pathology;
 - Single fibroid ≥ 4 cm or multiple (> 4) fibroids that measure ≥ 2 cm or symptomatic submucosal fibroid of any size.
- 23. Subject with a current history of undiagnosed abnormal genital bleeding.

8.5 Withdrawal of Individual Subjects

A subject will be withdrawn if ANY of the following criteria are met:

- The subject wishes to withdraw from further participation
- The subject is significantly noncompliant with the Protocol
- Continuing in the study would be detrimental to the subject's safety in the opinion of the Investigator, eg, the subject experiences a pretreatment event (PTE) or an AE that requires early termination (ET) because continued participation poses an unacceptable risk to the subject's health, or the subject is unwilling to continue because of the PTE or AE
- Subjects who become pregnant during the study should be withdrawn from study treatment. Refer to Section 12.9 for necessary documentation and procedures for following up with the subject
- Subjects who develop:
 - Hypersensitivity reactions, such as anaphylaxis and moderate to severe infusion-related reactions.
 - Abnormal hematologic indices as below:
 - White blood cell count (WBC) < 3000/mm3 (< 3.0×10^9 /L) or absolute neutrophil count < $1.500/\mu$ L
 - Platelets < 100,000/μL
 - Hemoglobin < 8 g/dL

Note: If a subject has a decline of hemoglobin to < 9 g/dL, hemoglobin will be repeated within 2 weeks.

- ALT or AST > 5 times ULN
- ALT or AST > 3 times ULN sustained for more than two weeks
- ALT or AST > 3 times ULN AND total bilirubin > 2 X ULN or international normalized ratio > 1.5

Note: If a subject experiences elevated ALT or AST \geq 3 times ULN, liver tests (ALT, AST, bilirubin, ALP, gamma-glutamyl transferase, and creatinine kinase) will be repeated within 3 to 5 days.

In addition, a subject may be withdrawn at any time for reason(s) other than those listed here. Medical monitor should be notified for all withdrawals.

If a subject is withdrawn prematurely from the study, the date the subject is withdrawn from the study and the reason for withdrawal will be recorded in the electronic Case Report Form (eCRF).

In case of withdrawal of a subject, the ET assessments should be performed per Table 2.

Reporting events as a SAE must be considered in cases where the AE has led to a withdrawal or the withdrawal is for a safety reason and, therefore, may be medically important, in

accordance with Section 12.

Any unresolved AE or SAE will be followed up according to Section 12.10.

In the event that a subject elects not to return to the clinical site for the ET Visit, the Investigator must make every effort to contact the subject to review all AEs. In the event that a subject drops out of the study at any time, the reason for discontinuation must be fully documented in the source documents and the eCRF. The Investigator site personnel will document the AEs and any other assessments in the source documents and will make every effort to complete all required ET assessments.

Subjects who are withdrawn from the study following randomization may not re-enter the study.

The study may be terminated by the sponsor at any time upon becoming aware of data that could compromise the safety and/or well-being of subject or for any other reason it deems appropriate.

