9.1.6 Unscheduled Visits

An unscheduled visit is defined as any visit to the Investigator site outside of the protocol specified time points due to safety reasons or when a repeated measurement is required (eg, obvious measurement errors, measuring device failure, confirmation of out-of-range results), where the subject is seen by study personnel.

Additional unscheduled safety assessments such as routine blood sampling may be performed at the discretion of the Investigator, if deemed necessary. All unscheduled visits and assessments performed during the visits will be recorded in the eCRF.

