10.18.2 Vital signs

Sitting blood pressure (systolic and diastolic) will be measured at all study visits, including Screening where vital signs are to be assessed. Sitting blood pressure will be measured using an automatic blood pressure recording device with an appropriate cuff size, after the subject has rested for at least 5 minutes in a sitting position. The same arm will be used for all measurements where possible. The Investigator will perform an overall evaluation of vital sign findings outside of the normal range for safety purposes; such results will be reported as either 'abnormal clinically significant (CS)', or 'abnormal not CS (NCS)'. Pulse rate and tympanic body temperature will also be measured. Abnormalities of clinical significance will be reported as AEs. Repeat measurements will be performed, if needed. In addition, at Visit 2, 5, 6 and 7, vital signs will also be measured at 15±5 minutes, 30±5 minutes and 60±10 minutes post study drug infusion.

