10.18.5 Routine Laboratory Evaluations

Blood and urine samples will be collected for routine clinical laboratory safety evaluations during the study are presented in Table 4.

Additional laboratory safety evaluations will be performed at other times, if judged clinically appropriate, or if the ongoing review of the data suggests a more detailed assessment of laboratory safety evaluations is required. Any changes to the scheduled times of laboratory safety tests will be agreed with the Sponsor and documented in the TMF.

The Investigator will perform a clinical assessment of all laboratory safety data.

Table 4 Routine Laboratory Evaluations

Hematology: Hemoglobin Hematocrit Platelet count Red blood cell (RBC) count Reticulocyte count	Mean corpuscular hemoglobin (MCH) Mean corpuscular hemoglobin concentration (MCHC) Mean corpuscular volume (MCV) White blood cell (WBC) count and differential	
Biochemistry: Alkaline phosphatase (ALP) Aspartate aminotransferase (AST) Alanine aminotransferase (ALT) Gamma-glutamyl transpeptidase (GGT) Potassium Sodium Chloride Inorganic phosphate Glucose Urea Bilirubin (direct and total)	Cholesterol Triglycerides High density lipoprotein-cholesterol (HDL-C) Low density lipoprotein-cholesterol (LDL-C) Protein (total) Albumin Creatine kinase Creatinine	
Coagulation: Prothrombin time International normalized ratio	Activated partial thromboplastin time	
Urinalysis: Specific gravity, pH, protein, glucose, ketones, urobilinogen, hemoglobin Microscopic examination ¹		

¹ Performed only if required, based on urinalysis results

Blood and urine samples will be performed by the Central Laboratory using standard methods. Procedures for the handling of samples will be described in full in a separate document.

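### The required 3–5 day liver retest in Protocol 8.5 leaves out INR, the only analyte in the liver withdrawal criteria that it does not cover

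*Protocol*

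**What the plan says.** Section 8.5 gives three liver criteria for mandatory withdrawal. One is ALT or AST above 5 × ULN. The second is "ALT or AST > 3 times ULN sustained for more than two weeks". The third is "ALT or AST > 3 times ULN AND total bilirubin > 2 X ULN or international normalized ratio > 1.5". A note below them sets the retest for any ALT or AST at or above 3 × ULN: "liver tests (ALT, AST, bilirubin, ALP, gamma-glutamyl transferase, and creatinine kinase) will be repeated within 3 to 5 days".

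Meeting a criterion has a direct consequence. Section 7.2.1 says "Subjects will receive no further dosing if they meet any of the withdrawal criteria listed in Section 8.5".

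INR is not absent from the trial. Table 4 in Section 10.18.5 has it in the routine panel ("Coagulation: Prothrombin time International normalized ratio"), and Table 5 in Section 10.18.6 plans 10 coagulation samples alongside 10 biochemistry samples.

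Other provisions allow or require follow-up without fixing an interval or naming INR:
- Section 10.18.5: "Additional laboratory safety evaluations will be performed at other times, if judged clinically appropriate".
- Section 9.1.6 allows unscheduled visits for "confirmation of out-of-range results".
- Section 12.6 requires clinically significant laboratory abnormalities to be followed until they resolve, stabilise or cease to be clinically significant. Section 12.10 is similar for adverse events.

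**The concern.** Both withdrawal and the stop on dosing depend on someone recognising that a criterion has been met. The retest is the one dated step the protocol requires between a raised transaminase and the next scheduled visit. It can confirm or refute the ALT/AST part and the bilirubin alternative of the combined criterion, but not the INR alternative. It does include ALP, GGT and CK, which appear in no liver criterion. The haemoglobin note in the same section, by contrast, repeats exactly the analyte that its criterion uses.

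At stake is a late finding of raised INR in a woman whose transaminases are already raised, possibly with another infusion due before the next dated INR result is known.

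**Working it through.** The plan states no figure on this point to reproduce. The check compares analytes, then dates.

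**Analytes (Section 8.5)**

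| Analyte | In a liver withdrawal criterion | In the retest panel |
|---|---|---|
| ALT, AST | yes | yes |
| Total bilirubin | yes | yes (as bilirubin) |
| INR | yes | **no** |
| ALP, GGT, CK | no | yes |

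INR is the only mismatch in the direction that matters.

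**Dates.** Inputs:
- Nominal days from SAP 7.3 (2): Week 1 = 8, Week 2 = 15, Week 4 = 29, Week 8 = 57, Week 12 = 85, Week 13 = 92, Week 16 = 113.
- Laboratory tests at each of these visits, from the safety visit table in SAP section 9.
- Infusions: Protocol 10.18.2 says "at Visit 2, 5, 6 and 7, vital signs will also be measured" after infusion. SAP 7.1.1.2 gives four doses at four-week intervals, hence Days 1, 29, 57 and 85.
- Assumption: INR is drawn at every laboratory visit.

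Gap to next dated INR = next nominal laboratory day − day of detection. Retest day = day of detection + 3 to 5.

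| Detection | Retest due | Next dated INR | Gap | Next infusion |
|---|---|---|---|---|
| Week 1, Day 8 | Day 11–13 | Day 15 | 15 − 8 = 7 | Day 29 |
| Week 2, Day 15 | Day 18–20 | Day 29 | 29 − 15 = 14 | Day 29 |
| Week 4, Day 29 | Day 32–34 | Day 57 | 57 − 29 = 28 | Day 57 |
| Week 8, Day 57 | Day 60–62 | Day 85 | 85 − 57 = 28 | Day 85 |

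For detection at Week 2, 4 or 8, the next dated INR falls on the day of the next infusion. With INR in the retest, the 7, 14, 28 and 28 days become 3–5. After Week 12 and Week 13 the gaps are 92 − 85 = 7 and 113 − 92 = 21 days. The last infusion is on Day 85, so these two gaps have no dosing consequence.

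**Two-week criterion.** The note's trigger is not limited to a first or a scheduled value, so a repeat that is still at or above 3 × ULN triggers another. Chains of 3-, 4- or 5-day steps first exceed 14 days at 5 + 5 + 5 = 15 days at the earliest and, for example, 5 + 5 + 4 + 5 = 19 days at the latest, after 3 to 5 draws. From detection at Week 1, 4 or 8 that is Day 23–27, 44–48 or 72–76. Each range ends before the next infusion on Day 29, 57 or 85. Read this way, the note already tests the duration criterion. It only leaves the repetition unstated.

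**The case against.** The strongest reply is that other provisions already cover the gap. With equal numbers of coagulation and biochemistry samples planned, INR is very likely measured with the scheduled sample that raised the alarm. Bilirubin is in the retest, so one of the two alternatives in the combined criterion is checked at 3–5 days. Sections 10.18.5 and 12.6 are worded as duties once clinical judgement is engaged. A value at or above 3 × ULN, in a woman who had to be below 2 × ULN at entry (exclusion 7), would very likely be judged clinically significant. Section 8.5 also lets the investigator withdraw a subject at any time.

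Most of this stands and keeps the point minor. What it leaves open is narrow: an INR on the triggering sample cannot show a later rise, and none of these provisions names INR or dates a repeat.

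A reader might go further and infer that the criterion of more than two weeks goes untested. The documents do not support that, because the natural reading of the note repeats the panel while the value stays raised. Week 2 looks like the awkward case, since Day 29 is exactly 14 days after Day 15. But a raised Day 29 value triggers its own repeat on Day 32–34, which is 17–19 days after Day 15.

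**Conclusion.** The point holds for INR: the required retest omits an analyte that a mandatory withdrawal criterion uses. On nominal days this leaves 7, 14, 28 or 28 days to the next dated INR after detection at Week 1, 2, 4 or 8, where 3–5 days is available at almost no cost. Explicit wording on repeating the panel is an optional clarification, not the correction of an error.

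The day counts assume that the trigger is a scheduled sample, that visits fall on their nominal days (the SAP window for Week 4 alone runs from Day 21 to 43), and that INR is drawn at every laboratory visit. The last cannot be confirmed. The SAP table gives 8 laboratory time points and Screening makes 9, while Table 5 plans 10. Table 2, the schedule of assessments, is not in the supplied text and may already hold a rule, so confidence is moderate.

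It would be wrong to infer that women with raised enzymes are unmonitored or that the INR criterion cannot be applied. Scheduled INR and the general follow-up duties remain. Sample size, power and the efficacy analysis are unaffected. Severity is minor: a cheap improvement.

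**What to change.** In the Section 8.5 note, add PT/INR to the panel repeated within 3 to 5 days. If Table 2 already requires it, a cross-reference is enough. At Table 5 volumes the cost is one 3 mL coagulation tube at a draw already required: 3 / 182.5 = 1.6% of the planned blood volume, only for women with ALT or AST at or above 3 × ULN.

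Optionally, add a sentence that the panel is repeated while ALT or AST stays at or above 3 × ULN, with at least one repeat more than 14 days after first detection. For a site that would otherwise stop at one repeat, a further full repeat takes 4 + 3 = 7 mL and one extra draw. The total is then 3 + 7 = 10 mL (10 / 182.5 = 5.5%). Keeping the 3–5 day interval until past 14 days would take 3 + 2 × 7 = 17 mL to 3 + 4 × 7 = 31 mL (9.3% to 17.0%), with 2 to 4 draws beyond the first repeat.

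No hold on infusions is proposed. If the sponsor wants one, Section 11.3 would need a written exception, because it does not allow dose timing to change.
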